7.1.2. Summary Measure

Mean treatment difference at week 12 after the first treatment

7.1.3. Population of Interest

The primary efficacy analyses will be based on the FAS1 population.

The exploratory analysis with PP population will be done. The analysis by using PP population is regarded as the sensitivity analysis for taking into account the study protocol compliance.

7.1.4. Strategy for Intercurrent (Post-Randomization) Events

Following strategy will be planned for intercurrent events. Note that these strategies will be applied for the data until 12 weeks after first administration.

Intercurrent Events	Strategy
Treatment discontinuation / Study withdrawal	
Considering the characteristics of study treatment, treatment discontinuation is not defined in this study.
 
In primary analysis, the missing data after study withdrawal will not be imputed and treated as missing. This means it is assumed that missing mechanism is missing-at-random for primary endpoint. In sensitivity analysis of assumed missing mechanism for primary endpoint, multiple imputation strategy by using placebo data (controlled imputation) will be done. This means it is assumed that missing mechanism is missing-not-at-random for primary endpoint. In this analysis. The missing data for GSK1358820 100U after treatment discontinuation will be imputed by using placebo data, while the missing data for placebo will be imputed by using placebo data. See "Handling of Missing Data for Statistical Analysis" in detail.

Use of protocol inhibited medication	
Not planned any specific handling for use of protocol inhibited medication. However, if many subjects (10% or more) used protocol inhibited medication until week12 after first treatment, additional sensitivity analysis might be done.

Intercurrent Events	Strategy
Use of rescue medication	Rescue medication is not defined in this study.

7.1.5. Statistical Analyses / Methods

Details of the planned displays are provided in [Appendix 10: List of Data Displays](#) and will be based on GSK data standards and statistical principles.

Unless otherwise specified, endpoints / variables defined in Section [7.1.1](#) will be summarised using descriptive statistics, graphically presented (where appropriate) and listed.

7.1.5.1. Statistical Methodology Specification

Endpoint / Variables

 Change from baseline in the daily average number of urinary incontinence episodes at week 12 after the first treatment 
 “Daily average” means “Daily frequency calculated by 3-day dairy”. More detail for calculation methods will be in section 11.6.2
Model Specification

 The endpoint will be analyzed using a mixed model for repeated measures (MMRM). Terms fitted in the MMRM model will include: 
 Fixed, categorical effects: treatment, site, visit, treatment-by-visit interaction Fixed, continuous effects: baseline daily average number of urinary incontinence episodes, baseline-by-visit interaction An unstructured variance structure will be used to model the within-subject errors, shared across treatments. The Kenward-Roger option in SAS PROC MIXED will be used to estimate denominator degrees of freedom and standard errors.
Model Checking & Diagnostics

 The Kenward and Roger method for approximating the denominator degrees of freedom and correcting for bias in the estimated variance-covariance of the fixed effects will be used. An unstructured covariance structure for the R matrix will be used by specifying ‘type=UN’ on the REPEATED line. Akaike's Information Criteria (AIC) will be used to assist with the selection of covariance structure.
Model Results Presentation

 Adjusted means (least square means: LS means) and corresponding standard errors (SEs) of means will be presented for each treatment by visit, together with estimated treatment differences (GSK1358820 – Placebo), the corresponding 95% confidence intervals and p-values. The primary treatment comparison will be the contrast between treatments at week

12 after the first treatment.

 Plots of LS means and SEs from the model will be generated for each treatment by visit.
Data included in Model

 The dataset including only data until week 12 after the first treatment will be used.
Subgroup Analyses

 Adjusted means and corresponding standard errors of means will be presented for each treatment at week 12 after the first treatment by each subgroup. MMRM model will be the same model as primary analysis. 
 Baseline UUI episodes over 3-day diary Age Sex BPH (only for male) Diabetes P- values for treatment- by -subgroup Interactions will not be calculated.
Sensitivity and Supportive Analyses

 In order to check robustness of primary statistical analyses, sensitivity analyses based on missing-not-at-random assumption will be performed. Missing data for the daily average number of urinary incontinence episodes will be imputed by controlled imputation methods (Mallinckrodt (2013)). The same MMRM as primary statistical analyses will be performed with imputed dataset. Adjusted means (LS means) and corresponding SEs of means will be presented for each treatment by visit, together with estimated treatment differences The dataset including only data until week 12 after the first treatment will be used.

7.2. Major Secondary Efficacy Analyses

7.2.1. Endpoint / Variables

The major secondary endpoint is change from baseline in the average volume voided per micturition at week 12 after the first treatment.

7.2.2. Summary Measure

Mean treatment difference at week 12 after the first treatment

7.2.3. Population of Interest

The major secondary efficacy analyses will be based on the FAS1 population.

The exploratory analysis with PP population will be done. The analysis by using PP population is regarded as the sensitivity analysis for taking into account the study protocol compliance.

7.2.4. Strategy for Intercurrent (Post-Randomization) Events

This strategy is the same as primary endpoint. Refer to [7.1.4](#).

7.2.5. Statistical Analyses / Methods

Details of the planned displays are provided in [Appendix 10](#): List of Data Displays and will be based on GSK data standards and statistical principles.

Unless otherwise specified, endpoints / variables defined in Section [7.2.1](#) will be summarised using descriptive statistics, graphically presented (where appropriate) and listed.

7.2.5.1. Statistical Methodology Specification

Endpoint / Variables

 Change from baseline in the average volume voided per micturition at week 12 after the first treatment.
Model Specification

 The endpoint will be analyzed using a mixed model for repeated measures (MMRM). Terms fitted in the MMRM model will include: 
 Fixed, categorical effects: treatment, site, visit, baseline UUI episodes over 3-day diary (<= 9 or >= 10), treatment-by-visit interaction Fixed, continuous effects: baseline average volume voided per micturition, baseline-by-visit interaction An unstructured variance structure will be used to model the within-subject errors, shared across treatments. The Kenward-Roger option in SAS PROC MIXED will be used to estimate denominator degrees of freedom and standard errors.
Model Checking & Diagnostics

 Same as the primary endpoint
Model Results Presentation

 Adjusted means (least square means) and corresponding standard errors of means will be presented for each treatment by visit, together with estimated treatment differences (GSK1358820 – Placebo), the corresponding 95% confidence intervals and p-values. Plots of LS means and SEs from the model will be generated for each treatment by visit.
Subgroup Analyses

 Same as the primary endpoint.
Sensitivity and Supportive Analyses

 In order to check robustness of major secondary statistical analyses, sensitivity analyses based on missing-not-at-random assumption will be performed. Missing data for the average volume voided per micturition will be imputed by controlled imputation methods (Mallinckrodt (2013)). The same MMRM as major secondary statistical analyses will be performed with imputed dataset.

CONFIDENTIAL

204947

- Adjusted means (least square means) and corresponding standard errors of means will be presented for each treatment by visit, together with estimated treatment differences
- The dataset including only data until week 12 after the first treatment will be used.

7.3. Other Secondary Efficacy Analyses

Other secondary endpoints include ones for both double blind phase and open label phase. For endpoint in open label phase, only summary statistics and no statistical analyses will be provided because treatment comparison is not of interest for open label phase.

7.3.1. Endpoint / Variables

- Changes from baseline and percentage change from baseline in the following endpoints
 - Daily average number of urinary incontinence episodes
 - Daily average number of urinary urgency incontinence episodes
 - Daily average number of voids
 - Average volume voided per micturition
 - Daily average number of urgency episodes
 - Daily average number of nocturia episodes (voids that interrupt night sleep)
- Urgency intensity
 - Change from baseline in daily average number of urgency episodes by each urgency intensity category
 - Proportions of patients with maximum urgency intensity
 - Change from baseline of maximum urgency intensity
- Proportion of patients attaining 100%, $\geq 75\%$ and $\geq 50\%$ reduction from baseline in the daily average of urinary incontinence episodes
- Proportion of patients attaining 100%, $\geq 75\%$ and $\geq 50\%$ reduction from baseline in the daily average of urinary urgency incontinence episodes
- Duration of treatment effect after 1st treatment
 - Time to qualification for retreatment
 - Time to request for retreatment
- Health outcome
 - Changes from baseline in King's Health Questionnaire (KHQ) domain scores
 - Proportion of patients with positive response on the Treatment Benefit Scale (TBS)
 - Changes from baseline in Overactive Bladder Symptom Score (OABSS) total score

7.3.2. Summary Measure

Mean treatment difference or odds ratio by visit, or hazard ratio for double blind period.

No treatment comparison for open label period.

7.3.3. Population of Interest

The secondary efficacy analyses will be based on the FAS1, FAS2 or FAS3 population, unless otherwise specified. Population will depend on TCs.

For change from baseline in daily average number of urinary incontinence episodes and average volume voided per micturition until 12 weeks after 1st treatment, PP population will be used for summary statistics.

7.3.4. Strategy for Intercurrent (Post-Randomization) Events

For binary data, DO=NR rule will be applied to missing data until 12 weeks after 1st treatment. For categorical data for maximum urgency intensity, baseline observed carried forward will be applied missing data until 12 weeks after 1st treatment. For time to event data, missing data will be treated as censor. All missing data for other secondary endpoints not mentioned above are treated as missing, will not be imputed, unless otherwise specified.

7.3.5. Statistical Analyses / Methods

Details of the planned displays are provided in [Appendix 10: List of Data Displays](#) and will be based on GSK data standards and statistical principles.

Unless otherwise specified, endpoints / variables defined in Section [7.3.1](#) will be summarised using descriptive statistics, graphically presented (where appropriate) and listed.

Note that statistical methodology will be applied to only TC1. Summary statistics will be provided for TC2 and TC3.

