### 5.3. Re-treatment Criteria

Patients can be considered for re-treatment beginning at the week 12 visit following the initial treatment or the week 12 visit following any re-treatment. The following re-treatment criteria must be used for the qualification of patient.

Qualification for re-treatment criteria:

- 1) Patient must have initiated request for re-treatment
- 2) Patient experienced  $\geq 2$  episodes of urinary urgency incontinence, with no more than one urgency incontinence-free day, as determined by the 3-day patient bladder diary completed in the week prior to the Qualification for Treatment visit
- 3) PVR urine volume must have been < 200 mL
- 4) Investigator deemed re-treatment appropriate and no condition or situation existed which, in the investigator's opinion (or sub-investigator's opinion), put the patient at significant risk from receiving a repeat treatment

Once these criteria are met, the patient who qualifies should be treated within 21 days of qualification, provided that all the following re-treatment criteria are met on the day of re-treatment.

Day of re-treatment criteria:

- 1) Central laboratory urine analysis for possible UTI using the sample collected at qualification for re-treatment visit had been reviewed by investigator (or sub-investigator)
- 2) Negative urine dipstick reagent strip test (for nitrites and leukocyte esterase)
- 3) Patient was asymptomatic for a UTI, in the opinion of the investigator (or sub-investigator)

- 4) Patient had discontinued any antiplatelet or anticoagulant therapy or medications with anticoagulative effects 3 days prior to re-treatment. Some medications may need to have been withheld for > 3 days per clinical judgment of the investigator (or sub-investigator)
- 5) Negative urine pregnancy test for women of childbearing potential.
- 6) Patient had initiated appropriate antibiotic medication 1 to 3 days prior to re-treatment
- 7) No occurrence of bladder stones since entry into the study
- 8) A minimum of 12 weeks (84 days) must have elapsed since the previous treatment
- 9) Period after 1st treatment did not exceed 36 weeks
- 10) Investigator (or sub-investigator) continued to deem a repeat treatment was appropriate and no condition or situation existed which in the investigator's opinion put the patient at significant risk from receiving a repeat treatment

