- Daily average number of nocturia episodes
- Daily average number of severe urgency episodes
- Daily average number of severe or moderate urgency episodes

Model Specification

- The endpoints will be analyzed using an analysis of covariance (ANCOVA) model.
- Terms fitted in the ANCOVA model will include:
 - Fixed, categorical effects: treatment, site, baseline UUI episodes over 3 day diary (<= 9 or >= 10)*
 - Fixed, continuous effects: baseline value

*; Baseline UUI episodes over 3-day diary (<= 9 or >= 10) is a stratification factor. This will be excluded for daily average number of urinary incontinence episodes and daily average number of urinary urgency incontinence episodes, because the strong correlation is expected between

Other Secondary Statistical Analyses for change from baseline and after week12 after first treatment
baseline values and a stratification factor.

 The Kenward-Roger option in SAS PROC MIXED will be used to estimate denominator degrees of freedom and standard errors.
Model Results Presentation

 Adjusted means (least square means) and corresponding standard errors of means will be presented for each treatment by visit, together with estimated treatment differences (GSK1358820 – Placebo), the corresponding 95% confidence intervals and p-values.

Other Secondary Statistical Analyses for change from baseline after first treatment
Endpoint(s)

 Change from baseline KHQ domain score (role limitations, social limitations) OABSS total score
Model Specification

 Same as "Other Secondary Statistical Analyses for change from baseline and percent change from baseline after week12 after first treatment".
Model Results Presentation

 Same as "Other Secondary Statistical Analyses for change from baseline and percent change from baseline after week12 after first treatment".

Other Secondary Statistical Analyses for Binary data
Endpoint(s)

 Proportion of subjects attaining 100%, $\geq 75\%$ and $\geq 50\%$ reduction from baseline in the daily average of urinary incontinence episodes Proportion of subjects attaining 100%, $\geq 75\%$ and $\geq 50\%$ reduction from baseline in the daily average of urinary urgency incontinence episodes
Model Specification

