
 The above endpoints will be analyzed using the Cochran-Mantel-Haenszel test (CMH test) stratified by a stratification factor at each visit
Model Results Presentation

 The number and percent of subjects who met each endpoint will be summarized by treatment and visit. The Mantel-Haenszel estimate of common odds ratio and its 95% confidence intervals will be estimated. The p-values by CMH test will be presented at each visit. Plots of proportion of subjects attaining 100% reduction will be generated for each treatment until week 12 after 1st treatment. As same for proportion of subjects attaining $\geq 75\%$ and $\geq 50\%$ reduction will be generated.
Handling Missing Data of Change from Baseline in the urinary diary

 If a subject has missing data due to any reasons (e.g., early withdrawal), then this subject will be regarded as NOT attaining 100%, $\geq 75\%$ and $\geq 50\%$ reduction from baseline in the daily

Other Secondary Statistical Analyses for Binary data

average of urinary (urgency) incontinence episodes (i.e., regarded as a non-responder). This rule will be applied to the data until week 12 after 1st treatment. Missing data after 12 week after 1st treatment will not be imputed and treated as missing.

- This rule will be called as “DO=NR” rule. DO=NR means dropout equals to non-responder.

Other Secondary Statistical Analyses for Binary data for TBS**Endpoint(s)**

- Proportion of subjects with positive response on the TBS

Model Specification

- The above endpoints will be analyzed using the Cochran-Mantel-Haenszel test (CMH test) stratified by a stratification factor at each visit

Model Results Presentation

- The number and percent of subjects who met each endpoint will be summarized by treatment and visit.
- The Mantel-Haenszel estimate of common odds ratio and its 95% confidence intervals will be estimated.
- The p-values by CMH test will be presented at each visit.

Handling Missing Data of TBS

- Missing data due to any reasons (e.g., early withdrawal) will be regarded as no positive response. This rule will be applied to the data until week 12 after 1st treatment. Missing data after 12 week after 1st treatment will not be imputed and treated as missing.
- This rule will be called as “DO=NR” rule. DO=NR means dropout equals to non-responder.

Other Secondary Statistical Analyses for Categorical data**Endpoint(s)**

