- Change from baseline of maximum urgency intensity
- Proportions of patients with maximum urgency intensity

Model Specification

- The above endpoints will be analyzed using van Elteren test stratified by a stratification factor at each visit

Model Results Presentation

- Change from baseline of maximum urgency intensity: The number and percent of subjects who met following category will be summarized by treatment and visit.
 - 3 point improvement
 - 2 point improvement
 - 1 point improvement
 - No Change
 - 1 point worsening
 - 2 point worsening
 - 3 point worsening
- For calculation of above category, the following values will be used for each intensity
 - 0: None
 - 1: Mild

Other Secondary Statistical Analyses for Categorical data

 ○ 2: Moderate ○ 3: Severe 
 ● Proportions of patients with maximum urgency intensity: The number and percent of subjects will be summarized by maximum urgency intensity category (None, Mild, Moderate or Severe) in the visit. No statistical test will be done for this endpoint. ● The p-values by van Elteren test will be presented at each visit for change from baseline of maximum urgency intensity.
Baseline Observation Carried Forward for Missing Data

 ● Missing data until week 12 after the first treatment will be imputed by baseline observation carried forward (BOCF). This rule will be applied to the data until week 12 after 1st treatment. Missing data after 12 week after 1st treatment will not be imputed and treated as missing.

Other Secondary Statistical Analyses for Time to Event data
Endpoint(s)

 ● Time to the subject's first request for 2nd treatment from the day of 1st treatment ● Time to the subject's first qualification for 2nd treatment from the day of 1st treatment
Model Specification

 ● The above endpoints will be analyzed using the log-rank test stratified by a stratification factor. ● The above endpoints will be displayed as Kaplan-Meier curves. ● In order to estimate the hazard ratio to placebo and its 95% confidence interval, Cox proportional hazard model will be used. This Cox model include treatment and a stratification factor as fixed effect.
Model Results Presentation

 ● The p-values by log-rank test will be presented. ● The hazard ratio to placebo and its 95% confidence interval will be estimated.

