11.4.1.1. Study Phases for Efficacy Data

Treatment State	Definition
Pre-Treatment	Date \leq 1st treatment Date
Treatment Cycle 1 (TC1)	1st treatment Date $<$ Date (if the subject completes / withdraws without 2nd treatment) \leq Study Exit/Withdraw Date or (if the subject take 2nd treatment) \leq 2nd treatment Date
Treatment Cycle 2 (TC2)	2nd treatment Date $<$ Date (if the subject completes / withdraws without 3rd treatment) \leq Study Exit/Withdraw Date or (if the subject take 3rd treatment) \leq 3rd treatment Date
Treatment Cycle 3 (TC3)	3rd treatment Date $<$ Date \leq Study Exit/Withdraw Date

NOTES:

- If the date of assessment of efficacy endpoint is the same as the date of 1st treatment, this can be regarded as prior to treatment according to study protocol.

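### From Week 18, TC1 tests listed as FAS1 use only subjects not yet re-treated who still have data; titles do not say so, and no full-FAS1 responder analysis is planned after Week 12

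*SAP*

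**What the plan says.** **Who is compared.** SAP section 4 defines FAS1 as all randomised subjects with at least one post-baseline efficacy assessment, and uses it for TC1 efficacy. SAP 7.3.5 limits testing: "Note that statistical methodology will be applied to only TC1. Summary statistics will be provided for TC2 and TC3". SAP 11.4.1.1 closes TC1 efficacy data at the second treatment date "if the subject take 2nd treatment", and 11.4.1 makes everything after that open label. SAP 7.3.2 sets the summary measure as "Mean treatment difference or odds ratio by visit, or hazard ratio for double blind period".

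**Who leaves.** Protocol 5.3 requires a request for re-treatment and at least two "episodes of urinary urgency incontinence, with no more than one urgency incontinence-free day, as determined by the 3-day patient bladder diary". It also requires a residual volume below 200 mL and the investigator's agreement.

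**Missing data.** SAP 7.3.4 applies DO=NR (dropout counted as non-responder) and baseline carried forward up to Week 12 only, and then says: "All missing data for other secondary endpoints not mentioned above are treated as missing, will not be imputed, unless otherwise specified". It names no strategy for re-treatment. For the binary and categorical endpoints SAP 7.3.5.1 adds: "Missing data after 12 week after 1st treatment will not be imputed and treated as missing". SAP 11.7.3 confirms that only observed data are analysed after Week 12.

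**What is tested after Week 12.** For the diary changes: "The endpoints will be analyzed using an analysis of covariance (ANCOVA) model". The reduction responders and TBS get a CMH test at each visit. For urgency intensity: "The p-values by van Elteren test will be presented at each visit for change from baseline of maximum urgency intensity".

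**Titles.** In SAP 11.10.6, Tables 2.9 (ANCOVA), 2.106, 2.110 and 2.114 (CMH after Week 12) and 2.120 (van Elteren) carry only the tag FAS1.

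**Change log and TBS.** Protocol 9.4.2 planned multiple imputation for the responder endpoints. SAP 2.1, Table 1, replaces it with DO=NR, on the ground that a subject missing at a visit is better taken as a non-responder. Neither text states a week limit. For TBS, SAP 11.6.3 counts a missing answer as no positive response, also without a week limit.

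**The concern.** A table tagged FAS1 invites the reader to take its percentages, odds ratios and mean differences as estimates for the arms as randomised. From Week 18 they describe the subjects who have not yet been re-treated, and re-treatment depends on how the subject is doing. A subject who is still leaking and asks for another injection drops out of the denominator, while a dry subject stays in it.

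The interim analysis, which covers data to 24 weeks, is made for regulatory submission (SAP 3.1 and Appendix 13). Its post-Week-12 comparisons, at Weeks 18 and 24, are of this kind. After Week 12 no planned reduction-responder table keeps re-treated subjects in the denominator, although the rationale in SAP Table 1 would point that way.

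**Working it through.** **Plan's own figures.** The only relevant figures are the Week-12 powers in protocol 9.2.1: 98%, 91% and jointly at least 89%. With 120 per arm and a non-central t calculation they come out at 97.6%, 91.1% and 88.7%. They agree, and this point does not touch them. The documents give no re-treatment rate and no responder rate.

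**Step 1: who is in the Week-18 tests.** Testing is confined to TC1, TC1 ends at the second treatment, and nothing is imputed after Week 12. The set is therefore FAS1, minus those already re-treated, minus those withdrawn or without a diary. A subject who qualifies at a visit still counts at that visit, and one re-treated at Week 30 still counts at Weeks 18 and 24.

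**Step 2: response status at the qualifying diary.** An urgency incontinence episode is a leakage record with urgency (SAP 11.6.3), so it is also an incontinence episode. With at least two of them, the subject is not a 100% responder on either endpoint. The other thresholds do not follow: two episodes from a baseline of 4 is a 50% reduction and from 8 a 75% reduction, and such a subject can still qualify.

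**Step 3: direction of the percentages (Tables 2.106 and 2.110).** Let R be the responders among those still in TC1, n the number of those with data, and m the number re-treated. The table shows R/n. The composite, with re-treated subjects counted as non-responders and other missing visits left out of both, is R/(n + m). Hence R/n ≥ R/(n + m) at every threshold. If other missing visits also count as non-response, the composite is lower still.

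**Step 4: direction of the odds ratio.** Suppose only non-responders leave, with fractions eA and eP of the active and placebo non-responders leaving. Then

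OR shown = OR full × (1 − eP)/(1 − eA).

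Illustration for a 100% endpoint, with all rates assumed: true response 25% v 10%, so OR full = (25/75)/(10/90) = 3.00.

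| Exit, active/placebo | eA, eP | Shown, active | Shown, placebo | OR shown |
|---|---|---|---|---|
| 20%/20% | 20/75 = 27%, 20/90 = 22% | 25/80 = 31.3% | 10/80 = 12.5% | (25/55)/(10/70) = 3.18 |
| 30%/36% | 30/75 = 40%, 36/90 = 40% | 25/70 = 35.7% | 10/64 = 15.6% | (25/45)/(10/54) = 3.00 |
| 30%/50% | 40%, 50/90 = 56% | 35.7% | 10/50 = 20.0% | (25/45)/(10/40) = 2.22 |
| 40%/70% | 40/75 = 53%, 70/90 = 78% | 25/60 = 41.7% | 10/30 = 33.3% | (25/35)/(10/20) = 1.43 |

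The percentages rise in every row. The odds ratio falls only where placebo non-responders leave more often than active ones.

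**Step 5: no treatment effect.** With 10% v 10% and 50% leaving each arm, the table shows 10/50 = 20% in both arms and an odds ratio of 1. The simulated CMH rejection rate is 5.0%.

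**Step 6: TBS.** SAP 7.3.5.1 leaves TBS missing after Week 12, which removes re-treated subjects from Table 2.114. SAP 11.6.3 counts missing as no positive response, which could keep them in the denominator. The SAP does not say which rule prevails.

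**The case against.** **The restriction is not hidden.** SAP 7.3.2 rules out comparisons in the open-label period, 7.3.3 says the population depends on the cycle, and 11.4.1 places everything after the second treatment in the open-label phase. The schedule heads Weeks 18 to 48 of phase 1 as applying to subjects not re-treated, and the descriptive tables are titled TC1. SAP 11.5.2 already asks for N and n with categorical data, and the mock shells are a separate document. All of this stands: a careful reader can work out the subset. What is missing is the wording on the test tables.

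**Much of the exit is visible at interim.** Table 1.2 gives disposition by epoch, Table 1.17 gives TC1 follow-up by arm in categories that include 12, 18 and 24 weeks, and Table 1.19 counts injections. This also stands, although none of them gives counts per efficacy visit.

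**A FAS1 analysis that uses re-treatment exists.** Time to request and time to qualification are analysed with a log-rank test, a Cox model and Kaplan-Meier curves (Tables 2.123 and 2.124). They come only at the final analysis and do not give response by visit.

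**The composite answers a different question.** It does. Some subjects who were ≥50% or ≥75% responders at qualification would be coded as non-responders. It belongs beside the planned tables and should not replace them.

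**Conclusion.** From Week 18 the listed FAS1 comparisons describe subjects not yet re-treated who still have data, and selection into that set depends on outcome. For Tables 2.106 and 2.110 the displayed percentages are at least as high as the full-FAS1 composite, by arithmetic. The odds ratio can move either way: from 3.00 to between 1.43 and 3.18 in the cases above, where every response and exit rate is assumed. The actual size cannot be known from the documents.

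Several stronger readings are tempting but not supported:

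- **The tables flatter the drug.** Equal or higher exit among placebo non-responders leaves the odds ratio unchanged or lowers it.
- **The tables overstate what would have been seen had nobody been re-treated.** The qualifying diary precedes the later visit, so this does not follow even for the 100% endpoints.
- **Every re-treated subject was a non-responder on all thresholds.** This holds only for the two 100% endpoints, at the qualifying diary.
- **Table 2.114 certainly shows the subset.** The two TBS rules leave that open.
- **Type I error or the main result is compromised.** If treatment affects neither response nor exit, the 5% level holds. The Week-12 primary and major secondary analyses are untouched, and these are other secondary endpoints without multiplicity adjustment.

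Severity: minor to moderate.

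**What to change.** 1. Add supportive CMH versions of Tables 2.106, 2.110 and 2.114 on the full FAS1 denominator. Count each subject as a non-responder from re-treatment onward, state a rule for other missing visits, and label the tables *response without re-treatment (composite)*.
2. Keep the planned CMH, ANCOVA and van Elteren tables and their p-values. Title or footnote them *FAS1 subjects not yet re-treated, observed data*, with n/N per arm and visit. The shorter label *subjects not re-treated* would be wrong, because subjects re-treated later still count at earlier visits. For Table 2.114 the label depends on item 3.
3. Reconcile SAP 11.6.3 with 7.3.5.1 so that missing TBS after Week 12, including after re-treatment, has one rule. Record the Week-12 limit on DO=NR in SAP Table 1.

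The cost is one derived flag, three extra tables, title or footnote edits and two text corrections. No planned analysis is removed. The supportive rates will be lower than those in the planned tables, and some re-treated subjects who met the 50% or 75% threshold at qualification will be counted as non-responders, which the footnote should say.
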